CT with contrast media enhancement has become the most accurate technique for diagnosing AMI, with a reported specificity between 90 and 100% [3,4], and is considered the first-line imaging modality when AMI is suspected. In addition to recognition of AMI, CT imaging has the potential to differentiate between reversible and irreversible ischaemic intestinal damage [5, 6]. **This is a pivotal moment in choosing the treatment strategy** – in the absence of irreversible damage; reperfusion therapy can restore intestinal viability and thus avoid bowel resection.

Various radiological signs are routinely used to detect bowel ischaemia in CT imaging. The list includes vascular – occlusion of mesenteric arteries or veins – and bowel signs – bowel dilatation, decreased or absent bowel wall enhancement, pneumatosis intestinalis, gas in the mesenteric or portal veins, and bowel wall thinning (Table 1). The capability of these signs to describe the stage of ischaemia has been addressed in some studies. A recent meta-analysis demonstrated that bowel wall thinning, decreased or absent bowel wall enhancement, bowel dilation, pneumatosis intestinalis, porto-mesenteric venous gas, and mesenteric artery occlusion are independent risk factors predicting transmural necrosis (5), whereas decreased or absent bowel wall enhancement and bowel dilation were predictive for

transmural necrosis also in venous occlusive AMI. The same meta-analysis showed that bowel wall thickening and increased bowel wall enhancement were not predictive of transmural necrosis (5). Importantly, while the specificity of these radiological findings, when considered individually, is considerably high—up to 98%—the sensitivity remains very low, ranging from 30% to 40% (5).

Based on this, we hypothesize that **combining multiple signs may enhance the diagnostic performance of CT scanning in distinguishing various stages of ischemic bowel damage.**

From a practical perspective, it is important to predict who **requires bowel resection** and who has **potentially salvageable bowel**. Bowel resection is a disabling surgery that significantly affects a patient's quality of life. Whenever possible, it should be avoided. If the bowel is salvageable, an endovascular procedure can restore mesenteric blood supply – this allows avoiding laparotomy and is considerably less traumatic for the patient.

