All CT findings with a univariate p -value ≤ 0.1 were entered into a multivariate logistic regression model to gauge their independent association with non-salvageable bowel damage (comparison 1) or confirmed diagnosis of AMI (comparison 2). The radiological score will be constructed based on univariate logistic regression models, where the dependent variable will be non-salvageable bowel and the independent variable will be radiological sign. The number of models will be equal to the number of radiological signs. The coefficient from the model will be uprounded and used as a weight for the radiological sign. In case the weights from the univariate models are clinically not relevant, expert opinions will be used instead. All the radiological signs will then be multiplied with the assigned weights and then summed. Finally, one by one the radiological signs will be left out of the score to test, whether a simpler version of the score would also give as good results as the more complicated version. The goodness of the score will be evaluated using AUC. A similar score will be constructed for suspected vs confirmed AMI.

However, if this will not result in a useful score, we will use a more complicated approach based on interactions between the radiological signs and interpretations of the results from the simpler approach.

In the first approach, **two scores** will be constructed.

- 1) using data of all patients with confirmed AMI
- 2) using data of only patients with confirmed arterial occlusive AMI

The performance of these two score will be tested in the following cohorts:

- a) all patients with confirmed AMI
- b) only occlusive arterial AMI included
- c) only non-occlusive AMI included
- d) Patients with venous occlusive AMI excluded
- e) Patients subjected to palliative care excluded

Table 1. Common radiological signs used to detect bowel ischaemia in CT imaging

	Radiological sign	Description
Vascular signs:		
1.	Occlusion of superior/inferior mesenteric artery/or its respective branches	No contrast enhancement on MDCT scan in the arterial phase or in the venous phase/lack of contrast enhancement within the vessel lumen / Acute arterial thrombi and emboli may appear as obvious low-attenuation filling defects in the SMA, its branches, or other major mesenteric arteries.

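### The score-weight rule gives no finite weight when a sign has a zero cell, leaving only an expert override without a criterion; rounding up, if meant literally, is also one-sided

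*Protocol*

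**What the plan says.** The Protocol, under Workout of radiological CT-score, builds the score from bowel signs 3 to 7 of Table 1. Each sign has its own univariate logistic model: "The number of models will be equal to the number of radiological signs". Then "The coefficient from the model will be uprounded and used as a weight for the radiological sign". The weighted signs are summed.

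The screen at p ≤ 0.1 does not govern these weights. Findings that pass it "were entered into a multivariate logistic regression model to gauge their independent association with non-salvageable bowel damage", and that multivariable model does not supply the points.

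Two later provisions bear on the weights:
- "In case the weights from the univariate models are clinically not relevant, expert opinions will be used instead"
- signs are left out one at a time to see "whether a simpler version of the score would also give as good results", judged by AUC.

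If the result is not useful, an approach based on interactions replaces it. One score is built on all confirmed AMI and another on arterial occlusive AMI only. In addition, "A similar score will be constructed for suspected vs confirmed AMI". The target under Allocation of patients into study groups is 50-100 salvageable and 50-100 non-salvageable patients.

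**The concern.** The primary objective is to create this score, so its points are the study's main product. The rule for setting them has two weaknesses.

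**Zero cell (main point).** The Background says that the specificity of single signs "is considerably high—up to 98%—the sensitivity remains very low, ranging from 30% to 40" per cent. With groups of this size, a sign that specific may not appear in any salvageable patient. The maximum-likelihood coefficient is then infinite, and whatever value the software prints depends on its stopping rule. The plan's only remedy for that weight is expert opinion. It does not say when a weight counts as clinically not relevant or how experts would replace it. The sign that discriminates best could thus receive a weight that another team could not reproduce.

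**Direction of rounding (secondary).** Read literally, rounding up gives 1 point to every odds ratio from just above 1 to 2.72 (e¹) and lifts mildly negative coefficients to 0. The error runs in one direction.

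**Working it through.** The protocol gives no figure for either point, so there is nothing to reproduce first.

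**Inputs**
- Group sizes of 50 and 100: Protocol, Allocation of patients into study groups.
- Specificity up to 98%, sensitivity 30-40%: Protocol, Background. These refer to transmural necrosis; that they carry over to resection is an assumption. Specificities of 95% and 90% are shown as a range.
- Prevalence of a sign with no association, 10-50%: an assumption, since the documents give none.
- Scope: signs scored present/absent. This covers signs 5 and 6 most directly, and signs 3, 4 and 7 once reduced to present/absent.

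**1. Zero cell.** P(no salvageable patient shows the sign) = specificityⁿ.

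| Specificity | n = 50 | n = 100 |
|---|---|---|
| 98% | 0.98⁵⁰ = 36% | 0.98¹⁰⁰ = 13% |
| 95% | 0.95⁵⁰ = 8% | 0.95¹⁰⁰ = 0.6% |
| 90% | 0.90⁵⁰ = 0.5% | about 0% |

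The size of the arterial-only group is not given. If it held 25 to 80 salvageable patients (half of 50 to four-fifths of 100, an assumption), the figures would run from 60% down to 20% at 98%, from 28% to 2% at 95%, and from 7% to 0.02% at 90%.

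**2. What the software returns.** Take a sign present in 17 of 50 non-salvageable (34%) and 0 of 50 salvageable patients. The maximum-likelihood coefficient is ln[(17 × 50)/(33 × 0)], which is infinite. Common fitting routines printed values from 13 to 35, and one failed. For a single 2×2 table, Firth's penalty equals adding 0.5 to each cell:
- 0 of 50: ln[(17.5 × 50.5)/(33.5 × 0.5)] = 3.97, weight 4 (or 2 × 3.97 = 7.93, weight 8, with a factor of 2).
- 1 of 50: the protocol's coefficient is ln[(17 × 49)/(33 × 1)] = 3.23, rounded up to 4. Firth gives ln[(17.5 × 49.5)/(33.5 × 1.5)] = 2.85, weight 3 (or 5.69, weight 6).

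One patient thus separates an ordinary weight of 4 from no estimate at all. Firth moves only from 3 to 4.

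**3. Rounding of a sign with no association.** Both groups were given the same prevalence and all pairs of binomial counts were enumerated exactly. The ordinary coefficient is ln[a(n − c)/((n − a)c)], where a and c are the non-salvageable and salvageable patients with the sign.

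| Rule | Positive weight | Any non-zero weight |
|---|---|---|
| Ordinary, rounded up | 43-47% | 47-51% |
| Ordinary, to nearest | 4-23% | 8-47% |
| Firth, to nearest | 4-21% | 8-43% |
| Firth × 2, to nearest | 18-35% | 36-69% |

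The ranges span 50 and 100 per group and prevalence 10-50%. Points under the factor of 2 are worth half a unit of log odds ratio. These figures precede the leaving-out step.

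**4. Cost of rounding to nearest.** For a sign with true odds ratio 1.5 (salvageable prevalence 10%, 30%, 50%), Firth to nearest gives no positive point in 57-64% of samples. Rounding up gives it a positive point in 69-91%.

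**The case against.** **Separation is a matter for the statistical analysis plan.** That plan is not shown, and silence on software options would be no finding. But the protocol itself fixes the estimator, fixes the rounding and names the remedy. What is criticised is a stated rule that cannot be carried out in a foreseeable case, with a stated fallback that has no criterion.

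**The 98% is an upper figure for another endpoint.** This stands. The salvageable group is defined by absence of resection, so unresected palliative patients may fall in it and show severe signs, which lowers specificity. At 95% with 100 patients the problem almost disappears. The risk concerns the most specific signs and the smaller analyses.

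**A reader might infer that a solver artefact would be published as a weight.** The documents do not support that. The override would probably catch an absurd value. The complaint is that its replacement follows no stated rule.

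**A reader might infer that a worthless sign will hold a point in nearly half of published scores.** That does not follow. The word may be a slip for ordinary rounding, and the 43-47% precedes the leaving-out step. In simulations under assumed scenarios, that step cut it to 24-30% with no AUC tolerance, or 6-13% with a tolerance of 0.01; the protocol states none.

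**A reader might infer that the protocol scores signs it already believes uninformative.** The Background does say that "bowel wall thickening and increased bowel wall enhancement were not predictive of transmural necrosis", and signs 4 and 7 mention both features. But they are only parts of those signs, the plan has one model per sign, and the Background lists the main feature of each of the five signs as predictive. Separate points for thickening and hyperenhancement cannot be assumed.

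**Rounding to nearest is itself a trade-off.** This also stands. It loses weak true signs, and with a factor of 2 a sign with no association gets some non-zero weight about as often as under rounding up, or more often at 50 per group, though each point is worth half as much.

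**Conclusion.** The zero-cell point holds and is the reason to act. For a present/absent sign with 98% specificity, the stated rule gives no finite weight in 36% of samples with 50 salvageable patients and 13% with 100. At 95% this falls to 8% and 0.6%. The chance is higher in the arterial-only score by an amount that cannot be fixed without its size. The figures assume that the cited specificity carries over from necrosis to resection.

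The rounding point is secondary and conditional. Under a literal reading, 43-47% against 4-23% shows a one-sided rule, given a present/absent sign at 10-50% prevalence. If ordinary rounding was meant, one word needs correcting.

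Neither point shows that the score would discriminate poorly, and the remedy should not be presented as raising AUC. What is at stake is whether the published points are finite, reproducible and drawn from the data. The change is worth making, but the defect does not invalidate the study.

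**What to change.** Replace the sentence on weights with a rule along these lines:

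- Estimate each sign's coefficient by Firth-penalised univariate logistic regression.
- Multiply by one scaling factor fixed in advance (for example 2) and round to the nearest integer, treating positive and negative values alike.
- Use the same rule for the all-AMI, arterial-only and suspected-versus-confirmed scores.
- Report any expert-opinion weights as a separately labelled alternative version beside the data-based one.

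This takes a few sentences, a standard software option and a little more analysis, with no new data.

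The choice of scaling factor has a price either way. Unscaled rounding to nearest drops weak signs and cost up to 0.007 AUC in one set of assumed scenarios and about 0.014 in another. A factor of 2 removes most of that loss (change of −0.0003 to +0.003 in the first set), but gives a sign with no association some half-unit weight in 36-69% of samples. Either choice is defensible if fixed before the weights are seen.

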The Feasibility of a Radiological Score Based on Quantified Analysis of Computed Tomography Signs for Recognizing Salvageable Bowel in Acute Mesenteric Ischemia: A Retrospective Analysis of Prospective Study

Primary study investigator: [name]. Department of Radiology, Tartu University Hospital, Estonia

Steering committee: [name], [name], [name], [name], [name], [name]

Synopsis

Computed tomography (CT) is the standard modality for scanning patients with critical acute abdominal conditions, including suspected acute mesenteric ischemia (AMI). CT imaging can potentially differentiate between reversible and irreversible ischaemic damage of the bowel. This moment is pivotal in selecting the treatment strategy for AMI – in the absence of irreversible damage; reperfusion therapy can preserve intestinal viability, thereby avoiding the need for bowel resection. The present study tests the hypothesis that combining several symptoms may enhance the diagnostic performance of CT scanning in detecting salvageable bowel in patients with AMI. This study is an ancillary component of the AMESI study (Clinical Trials: NCT05218863) – a prospective, multicentre observational study aimed at identifying the incidence and describing the outcomes of acute mesenteric ischemia (AMI) in adult hospitalized patients. The ultimate purpose of the present study is to create a computed tomography-based radiological score for the assessment of bowel viability in patients with AMI.

Background

Computed tomography (CT) is the standard modality for scanning patients with critical acute abdominal conditions, including suspected acute mesenteric ischaemia (AMI)(1). AMI is a disease with high lethality that is often difficult to diagnose due to non-specific symptoms and the absence of diagnostic biomarkers, and it lacks a standardized therapeutic concept. There are different types of AMI that can be differentiated by aetiology: arterial occlusion, venous occlusion and non-occlusive form of AMI. Non-occlusive mesenteric ischaemia (NOMI) occurs in patients with debilitating comorbid conditions such as shock, haemorrhage, surgery, dialysis, hypovolemia, cardiac disorders, pancreatitis, vasoactive treatments, intoxications, or intense exercise [2].

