The present study will elucidate whether the presence of five common radiological bowel signs on CT, either alone or in combination, may distinguish between no bowel ischaemia (suspected AMI) vs. reversible (AMI treated without bowel resection) vs. irreversible ischaemic damage (AMI treated with bowel resection).

To accomplish this, CT scans from patients enrolled in the multicentre international study (The AMESI study, Clinical Trials: NCT05218863) will be collected and subjected to retrospective analysis by the investigating radiologists. After analysing predefined radiological signs separately for their association with the need for bowel resection, the feasibility of combining different CT findings will be explored with the goal of **establishing a practical CT-based radiological scoring system for separating patients with reversible and irreversible bowel ischaemic damage.**

As different subtypes (arterial, venous, and non-occlusive mesenteric ischemia) have different pathoanatomical courses, differences in radiological bowel signs may be expected. To overcome this variability, we will first elaborate the score based on all patients with a confirmed diagnosis of AMI. As a second stage, we will test the score by including only patients with arterial occlusive AMI. If these two created scores appear to be different, we will test them mutually and in subgroups of other subtypes of AMI. The ultimate goal is to have one radiological score identifying the magnitude of bowel damage that could be used for any form of AMI, with possible minimized adaptations needed subtypes.

Considering the low number of venous AMI and NOMI we will primarily not create separate scores for these subtypes. If the performance of created scores appears insufficient in our study, these subtypes need to be assessed in a separate study.

Objectives

The primary objective of the study is to **create a CT-based AMI score using radiological signs that would enable the differentiation between patients with salvageable and non-salvageable ischemic bowel damage.**

The specific objectives are as follows:

- To describe the prevalence of common radiological bowel signs (Table) in AMI patients with and without irreversible ischaemic damage of the bowel.
- To assess the prognostic capability of these radiological bowel signs, both individually and in combination, for predicting irreversible ischaemic damage of the bowel.

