- To describe the prevalence of common radiological bowel signs in patients with confirmed AMI vs. suspected but eventually non-confirmed diagnosis of AMI
- To describe the prevalence of common radiological bowel signs in patients with different subtypes of AMI (arterial occlusive, venous, NOMI, other/unclear).

Study questions

- 1) What is the frequency rate of common radiological bowel signs (Table 1) among AMI patients with and without salvageable bowel?
- 2) Is it possible to distinguish the AMI patients with and without salvageable bowel with the use of a CT-based AMI score composed of common radiological signs?
- 3) Is it possible to differentiate the patients with and without AMI with the use of CT-based AMI score composed from common radiological signs?

Hypothesis

It is possible to differentiate between AMI patients with salvageable and non-salvageable ischemic bowel damage using the score based on CT radiological bowel signs.

Study outcomes

Primary study outcomes: Frequency rate of common radiological signs in AMI patients with and without salvageable bowel. Radiological score value in AMI patients according to the stage of bowel ischaemic damage.

Secondary study outcomes:

Frequency rate of common radiological signs/findings among patients with confirmed and suspected but eventually not confirmed AMI.

Performance of the radiological score in patients with different types of AMI.

Methods

This is a substudy of the AMESI study - "Incidence, Diagnosis, Management, and Outcome of Acute Mesenteric Ischaemia: A Prospective, Multicentre Observational Study." As of the end of August 2023, a total of 705 patients from 32 study sites worldwide have been enrolled, with 418 of them having confirmed cases of AMI. For patients with confirmed AMI, comprehensive data collection concerning diagnostics, management, and long-term outcomes has been completed (refer to Appendix 1).

Patients:

From the final AMESI cohort, we will select 6-7 sites limited to Europe due to logistical reasons related to the installation of software for the transmission of full CT investigations in impersonalized form. We expect to obtain images of at least 100 patients with confirmed AMI. Only study sites with more than 20 patients in total enrolled in the study will be asked to contribute radiological data. The CT scans will be gathered through AMESI's dedicated international online platform, and a retrospective visual and

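### The Synopsis and Background claim that combining CT signs improves on single signs, but no planned analysis compares the score with the best single sign

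*Protocol*

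**What the plan says.** The protocol words its hypothesis in two ways.

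- **Incremental.** The Synopsis says: "The present study tests the hypothesis that combining several symptoms may enhance the diagnostic performance of CT scanning in detecting salvageable bowel". The Background repeats the idea, that "combining multiple signs may enhance the diagnostic performance of CT scanning in distinguishing various stages of ischemic bowel damage". The reason it gives is that individual signs have specificity up to 98%, whereas "the sensitivity remains very low, ranging from 30% to 40" per cent.
- **Absolute.** The Hypothesis section reads: "It is possible to differentiate between AMI patients with salvageable and non-salvageable ischemic bowel damage using the score based on CT radiological bowel signs". It makes no reference to single signs.

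One specific objective covers both kinds of result: "To assess the prognostic capability of these radiological bowel signs, both individually and in combination, for predicting irreversible ischaemic damage of the bowel". It defines no contrast between them.

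The Statistics section (Workout of radiological CT-score) weights each bowel sign by its rounded-up univariate logistic coefficient and sums the weighted signs. It then removes signs one at a time to see whether a shorter score does as well. On performance it says: "The goodness of the score will be evaluated using AUC". Signs with univariate p ≤ 0.1 also enter a multivariable logistic model. A more complicated approach follows "if this will not result in a useful score", and no criterion is given for that judgement.

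**The concern.** An AUC for the score alone answers whether the score discriminates. It does not answer whether the score discriminates better than the best of its components, which is what the Synopsis and Background say is being tested. If one sign carries most of the information, the score's AUC can look respectable while combining contributes nothing.

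The stated clinical problem is also specific: single signs miss too many cases at high specificity. AUC averages over all specificities, so it does not show whether that problem has been reduced.

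At stake is the main message of the report. A reader told that combining signs helps would have no planned estimate of how much, and no guard against an apparent gain produced by deriving the weights and measuring the AUC in the same patients.

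**Working it through.** The protocol gives no target AUC, margin or sample-size calculation, so there is no figure to reproduce.

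**1. What a single sign already achieves.** Inputs, from the Background: sensitivity 0.30 to 0.40, specificity up to 0.98. For one binary sign, AUC = (sensitivity + specificity)/2.

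- Lower end: (0.30 + 0.98)/2 = 0.64
- Upper end: (0.40 + 0.98)/2 = 0.69

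This pairs each sensitivity with the highest quoted specificity. Each 0.02 taken off specificity lowers the AUC by 0.01.

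**2. What a score with no real gain would look like.** Assumptions: 50 or 100 patients per group (the protocol's target range), five binary signs (Table 1, items 3 to 7), one of them informative and four independent noise signs equally frequent in both groups. Weights are univariate log odds ratios rounded up. The noise prevalence (10% to 30%) and the independence are assumptions, not protocol figures.

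- Informative sign 40% vs 4%: true single-sign AUC = (0.40 + 0.96)/2 = 0.68. The mean apparent score AUC is about 0.70 to 0.73, depending on group size and on how negative coefficients are rounded. With weights rounded to the next higher integer, the same weights applied to new patients give 0.68, so the excess is optimism.
- Informative sign 30% or 40% vs 2%, noise prevalence 10% or 20%: the apparent score AUC exceeds the best single sign's by 0.02 to 0.06 on average, and is nominally higher in 84% to 99% of runs.

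**3. What the planned checks would show in such data.**

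- Leave-one-out: dropping some sign leaves the AUC as high or higher in 74% to 100% of these null runs, against 0% to 11% when all five signs are informative. It is a real warning signal. Applied repeatedly, however, dropping a sign whenever the AUC does not fall, it ends at one sign in only 8% to 14% of null runs.
- Multivariable model: after the p ≤ 0.1 screen, a noise sign reaches p < 0.05 in about 5% to 16% of runs. The model would usually point to the one strong sign, but the plan attaches no consequence to this.

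**4. Whether the missing contrast is feasible.** With five equally informative independent signs, the AUC gain over the best single sign is about 0.22 to 0.23, and a paired 95% interval detects it in every run at 50 and at 100 per group. This is a favourable case; correlated signs would give a smaller gain.

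**The case against.** The strongest reply is that the plan is not confined to the score's AUC. The leave-one-out step compares the score with shorter versions in the same patients, the multivariable model looks at independent contribution, and the objectives cover signs individually as well as combined. The formal Hypothesis is absolute, and an AUC does address it. Tests and thresholds for AUC differences are often left to an SAP, which is not at hand.

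Most of this stands, and it rules out a stronger reading that a reader might infer: that the score is judged by its AUC alone, so that a worthless score would almost always appear to confirm the hypothesis. The documents do not support that reading, for three reasons.

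- The two further checks exist and would often reveal redundancy.
- The protocol nowhere says that an AUC interval above 0.5 confirms anything, so a pass rate under such a rule measures a rule that is not in the plan.
- The scenario with four noise signs is extreme. The Background cites wall thinning, reduced or absent enhancement, dilatation, pneumatosis and porto-mesenteric gas as independent predictors of transmural necrosis.

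The gap itself remains. Leave-one-out has no margin, stopping rule or single-sign endpoint; the multivariable model has no decision rule; and assessing signs both ways is not comparing them. The protocol itself fixes the performance measure and words the hypothesis in two ways, so the mismatch lies in its stated text and is not a detail deferred to the SAP.

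**Conclusion.** The point holds in a limited form. The incremental hypothesis of the Synopsis and Background has no analysis that compares the score with the best single sign, and it differs from the hypothesis in the Hypothesis section. On the protocol's own figures, a score AUC of 0.64 to 0.69 would be no better than one sign. Under the extreme noise assumption, even 0.70 to 0.73 could be apparent gain only.

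The 0.64 to 0.69 range assumes that the quoted sensitivities and the top quoted specificity belong to the same sign. It also assumes that figures for transmural necrosis carry over to this study's grouping by bowel resection. The simulated figures show what the plan could fail to detect; they do not predict the result. The planned AUC remains a fair answer to the weaker, absolute hypothesis.

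**What to change.** 1. **Align the wording** of the hypothesis in the Synopsis, Background and Hypothesis sections, so that it is clear whether the claim is that the score differentiates or that combining improves on single signs.
2. **Add the contrast** to the Statistics section: the paired AUC difference, score minus best single sign, in the same patients, corrected for optimism and reported with an interval. Each bootstrap resample should repeat the weighting, rounding, cut-off choice (Table 1 derives dilatation cut-offs from the data) and choice of best sign. The resulting score and sign are then tested back on the full sample to estimate the optimism to subtract.
3. **Report the score's sensitivity at the best single sign's specificity**, which speaks directly to the weakness named in the Background.
4. **Claim that combining helps only on the basis of this corrected comparison.**

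The correction is essential. In simulated null data, a bootstrap that repeats score building without it put the lower limit of the AUC difference above 0 in about 24% to 38% of runs (rounding to the next higher integer) or 72% to 82% (rounding away from zero). With optimism correction this fell to about 6% to 19%. Because that is still not negligible, the corrected lower limit should not serve as a stand-alone definition of a useful score.

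The cost is a few sentences of protocol text and slightly more programming, with no new data. The downside for the sponsor is that the claim becomes harder to meet.
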